SmPC	Summary of Product Characteristics
TEAE	Treatment-emergent adverse event
TSAT	Transferrin saturation
WMA	World Medical Association

1. INTRODUCTION AND BACKGROUND

1.1 Background of the Disease and Treatment Options

Iron deficiency (ID) is one of the most commonly known forms of nutritional deficiencies. Iron deficiency is a state in which there is insufficient iron to maintain the normal physiological function of tissues such as the blood, brain, and muscles. As iron is present in all cells and, as part of enzymes, is essential for numerous vital functions, such as oxygen transport, transport of electrons in the form of cytochromes, impaired physical condition, cognitive impairment, disturbed thermoregulation and fatigue have been described in patients with ID [1].

Iron deficiency is usually only detected when untreated ID has led to anaemia. Iron deficiency is considered the primary cause of anaemia in approximately 50% of cases [3]. Low haemoglobin (Hb) levels, in conjunction with a decrease in erythrocyte volume and a low erythrocyte Hb concentration (microcytic, hypochromic anaemia), are indicative of iron deficiency anaemia (IDA). Additional assessments include iron makers, such as serum ferritin, a cellular iron-binding protein which is also secreted into the blood, providing the most reliable indirect measure of body iron stores in the absence of infection or inflammation. Serum ferritin levels below 15 ng/mL are highly specific for empty iron stores. Values from 15-30 ng/mL correspond to empty to limited iron stores; values from 30 to 50 ng/mL are borderline and values above 50 ng/mL without coexisting inflammation/infection are evidence of sufficient iron reserves [3].

Although a modern diet and the use of iron supplements have reduced the incidence and degree of ID in industrialised countries, iron supply is still a problem in certain subgroups of the population, namely young children, pregnant and menstruating women. The prevalence of iron deficiency that resulted in iron deficiency anaemia (IDA) in China, is estimated to range from 19.9% to 28.9%, dependent on the population studied, and considered a moderate public health concern [3]. Additionally, ID may be observed in patients with chronic diseases where hepcidin is upregulated and appears to decrease absorption of iron from the gastrointestinal tract (e.g., chronic kidney disease (CKD), chronic heart failure (CHF) or inflammatory bowel disease (IBD)). For instance, it has been demonstrated that ID alone is an independent risk factor for mortality in patients with CHF [4].

Mild ID (i.e., plasma ferritin <30 ng/mL, transferrin saturation (TSAT) <20% [5]) can be prevented or corrected by eating iron-rich foods. However, as ID can have serious health consequences that diet may not be able to quickly correct, iron supplementation may be necessary. Initial treatment options usually include oral iron replacement therapies. Unfortunately, there is a subset of patients where oral iron is ineffective or cannot be tolerated and intravenous (IV) iron replacement is required.

Typically, oral iron is not effective in populations that have an underlying chronic disease that may be impairing absorption of iron from food (or other oral supplements)

[figure not shown]
or where the loss is greater than amount that can be replaced or there is a need for a more rapid repletion than can be achieved with oral iron. Diseases that may lead to impaired absorption have resulted in numerous international guidelines being developed to aid in guiding physicians for appropriate correction measures. Examples of where IV iron is recommended include CKD [6], IBD [7] and oncology [8].

Iron Sucrose (IS, Venofer[®]) is an IV iron replacement therapy approved in China. This was first approved in China in 2008 and is used in patients in whom the results following oral administration of iron preparations are not good and who require IV iron therapy. It is recommended that the iron deficit is calculated with the Ganzoni formula [9] and thereafter corrected with individual bolus IV injections/ infusions of up to 200 mg iron administered.

1.2 Summary of Ferric Carboxymaltose Nonclinical and Clinical Data

1.2.1 Pharmacology

Ferric carboxymaltose (FCM, Ferinject[®]) is a polynuclear iron(III)-hydroxide carboxymaltose complex with a molecular weight of about 150,000 Daltons.

1.2.2 Preclinical and Pharmacokinetic Studies

In pharmacokinetic (PK) studies after IV administration in Caucasian subjects, iron provided by FCM was rapidly cleared from the serum and efficiently incorporated into erythrocytes [10]. Iron from FCM was distributed predominantly to the liver, spleen and bone marrow [11]. Non-clinical studies showed that, in the liver, which is a primary site for iron storage, IV administration of FCM resulted in iron localisation predominantly in cells of the reticuloendothelial system (RES), with minor amounts in the parenchyma [12]. The deposition of iron in the RES (phagocytes/monocytes) is preferred as it minimises the potential for iron-induced oxidative damage to the parenchyma, as described in mice with different IV iron preparations [13].

It is to be considered that the findings observed in the various toxicological studies resulted from iron overload in healthy iron-replete animals. Iron accumulation could be seen predominantly in the liver, spleen and kidneys when repeated high doses were administered to rats and dogs. Repeated-dose toxicity studies in rats and dogs indicate that in terms of total iron dose, there is about a 3- to 8-fold safety margin to the human dose based on the no observed adverse effect level.

Data from reproductive and developmental toxicity studies indicate that there is a minimal risk associated with administration of FCM during pregnancy and lactation. Nonclinical studies suggested that there is limited placental or milk transfer of iron

from FCM after maternal exposure to FCM. Therefore, the use of FCM is contraindicated in the first trimester of pregnancy, and the potential risks and benefits should be carefully balanced when considering use of FCM in pregnant women in the second and third trimester, or lactating women.

Ferric carboxymaltose did not demonstrate genotoxic potential in a standard battery of tests.

Ferric carboxymaltose did not exhibit cross reactivity with anti-dextran antibodies in a guinea pig passive cutaneous anaphylaxis model. Administration of a challenge dose of FCM to previously treated rats did not result in a hypersensitivity reaction.

Based on these nonclinical studies, FCM is considered to have a suitable pharmacologic, toxicologic and safety profile for IV dosing in humans for the treatment of ID/IDA.

1.2.3 Efficacy

In general, clinical safety and efficacy studies have been conducted in numerous settings representative of underlying diseases that may lead to ID; i.e., diseases with increased inflammatory status impairing iron absorption as well as diseases with increased losses of iron that cannot be compensated via dietary iron. Single iron doses administered to subjects ranged from 100 mg to 1,000 mg iron, with cumulative iron doses of up to 6,500 mg administered for repletion and maintenance of iron stores. More specifically, studies have been conducted in conditions leading to ID/IDA using distinct populations in nephrology, women's health, gastroenterology, cardiology, and neurology, as well as combinations of various populations. Data of 7,300 subjects treated with FCM in 38 clinical trials have been generated so far. No studies have been performed in healthy volunteers due to the fact that FCM is designed to replenish deficient iron deposits, and as iron cannot be excreted, administration to healthy non-iron deficient volunteers may be toxic.

Across the various clinical studies performed, effective replenishment of iron stores has been consistently observed. Markers of ID have included both TSAT and serum ferritin. In subjects with more severe or prolonged ID with associated anaemia, correction of ID using FCM has consistently resulted in significant increases in Hb values (correction of anaemia). An increase in Hb values was usually seen within 4 weeks of FCM administration. In addition to the correction of laboratory parameters, iron replacement therapy has demonstrated significant improvements in quality of life and functional and symptomatic status in some patient populations. Of importance, these latter improvements were also seen when FCM was administered to ID subjects without anaemia, with no significant changes (either increase or decrease) to Hb values.

Ferric carboxymaltose first received marketing authorisation in The Netherlands in July 2007, and since then, in over 60 countries worldwide. The total exposure of

patients since the introduction of FCM into the market up to 1 January 2015 corresponds to over 2,179,768 patient years. The total number of adverse drug experience cases reported is considered small with respect to the overall drug exposure. The reports confirm the known adverse event (AE) profile and the positive benefit/risk ratio of FCM.

1.2.4 Safety

Ferric carboxymaltose was well tolerated by study participants. In completed clinical studies, up to 1 January 2015, approximately 50% of the subjects experienced at least one treatment-emergent adverse event (TEAE), and events considered related to treatment occurred in 17.5% of subjects who received FCM. Overall, the most commonly reported adverse drug reactions (ADR) in the FCM group were nausea, headache, dizziness, hypertension, injection/infusion site reactions, hypophosphataemia and flushing. Only 1.7% of subjects had severe TEAEs.

In relation to laboratory parameters recorded in clinical studies, no consistent pattern of clinically meaningful changes requiring intervention have been observed. However, mild and transient changes of liver enzymes, such as aspartate aminotransferase (AST and alanine aminotransferase (ALT), gamma-glutamyl transferase (GGT and alkaline phosphatase (AP, have been reported in some studies.

A transient decrease in blood phosphorus levels was frequently observed. The nadir occurred approximately 2 weeks after dosing and resolved without treatment in most subjects within the follow-up period of up to 12 weeks. Severe hypophosphataemia (i.e., <0.3 mmol/L) was only observed in very few cases, and was of short duration.

A human breast milk excretion sub-study suggests a low toxic potential for infants breastfed by mothers receiving FCM (Study VIT-IV-CL-009). Higher iron levels in breast milk were measured 24 and 48 hours after IV administration of FCM compared with ferrous sulphate, however all levels of iron measured were considerably lower than toxic levels that could result in iron intoxication of the newborn. Transfer of iron from FCM to human milk was $\leq 1\%$. Based on limited data on nursing women, it is unlikely that FCM represents a risk to the nursing child.

The safety profile of FCM in the first trimester of pregnancy has not been demonstrated in a clinical trial. There is, however, a limited amount of data from a recent clinical study (FER-ASAP-2009-01) in which no new safety signals were observed for mother and child after administration of FCM (n=123) for the treatment of IDA in the second and/or third trimester of pregnancy. A careful benefit/risk evaluation is required before FCM use during pregnancy. If the benefit of FCM treatment is judged to outweigh the potential risk to the foetus, it is recommended that treatment be confined to the second and third trimester of pregnancy.

As with all parenteral iron preparations the absorption of oral iron is reduced when administered concomitantly. No formal interaction studies have been performed.

Refer to the Investigator's Brochure (IB) for further details.

2. RATIONALE

Ferric carboxymaltose has been developed by Vifor Pharma – Vifor International Inc. as a formulation enabling the application of high iron doses of up to 20 mg/kg body weight as infusion, and as undiluted injection of up to 15 mg/kg body weight. Ferric carboxymaltose has a low immunogenic potential and does not exhibit cross-reactivity to anti-dextran antibodies. The application of high doses of IV iron in 1 single administration with the potential to replenish the iron stores has multiple advantages over multiple smaller doses. Compared to other IV iron products, FCM can be given in a short time (6 minutes instead of 3.5 hours for a 500 mg iron dose) and in iron doses of up to 1,000 mg, which reduced the need for the subject for multiple and long stays at the hospital. This reduces hospital costs [5]. Also, especially in rural regions, a single administration for replenishing the iron stores may help to increase subject compliance, and might make long journeys to the hospital unnecessary. A single administration versus multiple infusions additionally reduces the risks associated with the administration procedure, such as phlebitis, infection, extravasation, of other infusion-related AEs [5].

It has been seen that interethnic variability in PKs of certain drugs can cause unexpected outcomes, such as therapeutic failure, adverse effects, and toxicity in subjects of different ethnic origin, which can be both due to genetic and environmental factors. The International Conference on Harmonisation (ICH) published a guidance to facilitate the registration of drugs among ICH regions (European Union, Japan, the United States), recommending a framework for evaluating the impact of ethnic factors on efficacy and safety of drugs at a particular dosage and dosage regimen. Especially drugs metabolised via the Phase 1 enzymes of the cytochrome group are prone to ethnical and/or genetic variability [14]. Ferric carboxymaltose is not metabolised via cytochrome and constitutes a delivery system for the trace element iron. Based on limited data from Asian subjects who participated in the global registration studies conducted in Europe, genetic or interracial differences are not expected.

According to the “Reform Plan for Chemical Drug Registration Classification ([2016] No. 51)” issued by the China Food and Drug Administration (CFDA) and effective since 04 March 2016, FCM constitutes a Category 5.1 drug, Originators marketed overseas under application for being listed in China. And according to requirement of clinical trials for products that are marketed overseas but not in China (CFDA order 28, Provisions for Drug Registration), a PK study should be conducted together with a 100-pair phase 3 study. This Phase 3 bridging study is designed to assess safety of FCM in the Chinese population, and to show efficacy by demonstrating non-inferiority to IS (Venofer), an IV iron product which is currently available on the Chinese market. A Phase 1, ascending dose study, VIT-IRON-2011-003, will be conducted in parallel to this Phase 3 study. The objective of this study is to evaluate the PK and pharmacodynamics of FCM in Chinese subjects with IDA.

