Design:	
Open-label, randomised controlled study to assess the impact of FCM in correcting IDA compared with Venofer (IS).
 
All subjects, after providing written informed consent and meeting the eligibility criteria, will receive a first dose of IV iron as either FCM or IS. A total of approximately 368 subjects (184 per group) will be randomised. All subjects will have IDA as measured by haemoglobin (Hb), serum ferritin and transferrin saturation (TSAT) at screening.
 
Ferric carboxymaltose will be administered as either a diluted infusion or undiluted injection (at Investigator's discretion) at single, maximum daily doses of 500 or 1,000 mg iron) and IS will be administered as an undiluted bolus push injection or diluted infusion (with each single injection/infusion of 200 mg iron). Note, for subjects randomised to receive IS, dosing visits are required three times a week to achieve total iron repletion dosing as calculated using the Ganzoni formula.
 
For subjects randomised to FCM, the total iron requirement will be calculated at baseline based on the screening Hb and body weight (BW). Dosing will be at baseline (Day 1) and, if required, at Day 8 and Day 15..

Design (Cont'd):	All subjects will attend study visits at screening, baseline and thereafter at Weeks 2, 4 and 6. All subjects will attend an end of study visit (at Week 8 – or earlier if discontinued prematurely). Additional dosing visits may be required for subjects receiving IS three times weekly up to Week 4.																														

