7.2 Drug Dosage and Administration

7.2.1 Arm A: Ferric Carboxymaltose

Study drug should be administered in doses based on subject BW and Hb value at screening as per Table 2.

Subjects will receive study drug as undiluted injection or infusion. The individual dose requirement (in mg of iron) per visit is described below:

Table 2: FCM Dosing Schedule

	Total Iron (mg) as FCM				
	BW 35 - <70 kg ¹		BW ≥70 kg		
	Hb <10 g/dL	Hb ≥10- <14 g/dL	Hb <10 g/dL	Hb ≥10- <14 g/dL	
Day 1	1,000 mg	1,000 mg	1,000 mg	1,000 mg	
Day 8	500 mg	No dose	1,000 mg	500 mg	

Notes: BW = Body weight; FCM = Ferric carboxymaltose; Hb = Haemoglobin.

1. The maximum single dose that should be given to a subject is 20 mg/kg BW, therefore for subjects with BW 35 - <50kg and Hb ≥ 10 g/dL, the 1,000 mg dose should be split into 2 x 500 mg (one 500 mg dose on Day 1 and one 500 mg dose on Day 8. Subjects with BW 35 - <50 kg and Hb < 10g/dL should receive 3 doses of 500 mg (on Day 1, 8 and 15).

For IV injection, the required amount of FCM solution will be drawn from the vial into a syringe and injected as an undiluted solution.

For drip infusion, FCM solution must be diluted only in sterile 0.9% m/V sodium chloride solution (500 mg iron diluted in 100 mL 0.9% w/v physiological saline, for a total volume of 110 ml or 1,000 mg iron diluted in 250 mL 0.9% w/v physiological saline, for a total volume of 270 ml). For stability reasons, dilutions to concentrations less than 2 mg iron/mL are not permitted.

From a microbial point of view, FCM preparations for parenteral administration must be used immediately after dilution with sterile 0.9% m/V sodium chloride solution.

For both injection and infusion, FCM should be administered up to a maximum single dose of 1,000 mg iron (up to a maximum of 20 mg/kg BW) over at least 5 minutes for the 500 mg dose and over at least 15 min for the 1,000 mg dose. Administration time should not exceed 30 minutes for either the 500 or the 1,000 mg dose.

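### The protocol gives two per-kilogram maxima for undiluted FCM injection, so a 1,000 mg injection at 50 to under 66.7 kg follows Section 7.2.1 but exceeds the figure in Section 2

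*Protocol*

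**What the plan says.** **Section 2 (Rationale)** separates the two routes. It describes FCM as a formulation that allows "high iron doses of up to 20 mg/kg body weight as infusion, and as undiluted injection of up to 15 mg/kg body weight".

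**Section 7.2.1 (Arm A)** does not separate them. It treats the two alike: "injection and infusion, FCM should be administered up to a maximum single dose of 1,000 mg iron (up to a maximum of 20 mg/kg BW". The footnote to Table 2 uses the same ceiling to decide who has the first dose divided: "The maximum single dose that should be given to a subject is 20 mg/kg BW, therefore for subjects with BW 35 - <50kg" the dose is given in 500 mg portions. From 50 kg upward, Table 2 gives 1,000 mg on Day 1 in every haemoglobin column.

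**Other places.** The Synopsis repeats the Table 2 footnote. Section 2.2 cites 20 mg/kg as the approved single-dose maximum without naming a route. SAP 1.1 restates the rationale with 20 mg/kg and omits the injection figure.

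**Route.** According to the Synopsis (Design), FCM "will be administered as either a diluted infusion or undiluted injection", and the choice is left to the investigator. Section 7.2.1 also permits both routes.

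**The concern.** A per-kilogram maximum for the investigational drug appears in two forms in one protocol, and ordinary conduct can reach the disagreement: undiluted injection is allowed, and 1,000 mg is the standard first dose from 50 kg.

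The practical consequence lies in safety reporting. Protocol 10.1.7 and SAP 4.7.1 define medication overdose by reference to the protocol's own maximum dose. Section 7.6.1 requires inadvertent overdosing to be reported as an adverse event. Section 10.3.2 sets reporting times for special situations: 5 working days, or 24 hours if a seriousness criterion is met. With two figures for an injected dose, the text leaves room for doubt about which maximum that definition refers to. Safety of FCM against iron sucrose is a secondary objective (Section 3.2), so the doubt falls on the arm under assessment.

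The SAP would not bring the matter to light. The FCM dosing codes in Appendix 1 cover schedule, dose by body weight and haemoglobin, administration time and dilution volume. None is tied to a mg/kg limit by route. The exposure summary in SAP 4.5 does not tabulate mg/kg by route.

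**Working it through.** **Inputs**

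- Ceiling for undiluted injection in Section 2: 15 mg/kg.
- Ceiling for infusion in Section 2: 20 mg/kg.
- Ceiling for both routes in Section 7.2.1: 20 mg/kg, and 1,000 mg per dose.
- Day 1 dose in Table 2: 1,000 mg from 50 kg; 500 mg from 35 to under 50 kg.
- Day 8 dose in Table 2: 1,000 mg only at 70 kg or more with Hb below 10 g/dL; otherwise 500 mg or none.

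**Formulae.** Weight threshold = dose / per-kilogram ceiling. Dose per kilogram = dose / weight.

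**Step 1: reproduce the protocol's own threshold.** 1,000 / 20 = 50.0 kg. This matches the footnote, which splits the dose below 50 kg, so the dosing table was built on 20 mg/kg for both routes.

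**Step 2: repeat with the Section 2 injection figure.** 1,000 / 15 = 66.67 kg.

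**Step 3: a single 1,000 mg dose by weight**

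| Weight (kg) | mg/kg | Within 20? | Within 15? |
|---|---|---|---|
| 50 | 20.0 | yes | no |
| 55 | 18.2 | yes | no |
| 60 | 16.7 | yes | no |
| 65 | 15.4 | yes | no |
| 66.7 | 14.99 | yes | yes |
| 70 | 14.3 | yes | yes |

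The 65 kg row is the protocol's own worked example in Section 2.1, where the first dose is 1,000 mg. That section does not say whether the dose is injected or infused.

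**Step 4: the remaining doses.** A 500 mg dose is at most 500 / 35 = 14.3 mg/kg, within both figures by either route. A 1,000 mg dose on Day 8 is given only from 70 kg, so it is at most 1,000 / 70 = 14.3 mg/kg, also within both. Any 1,000 mg infusion from 50 kg upward is at most 20.0 mg/kg, which both sections allow.

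The disagreement is therefore confined to the Day 1 dose of 1,000 mg, given as undiluted injection, at 50 to under 66.7 kg.

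**The case against.** The strongest reply is that Section 2 is background. Its sentence describes what the formulation makes possible, whereas Section 7.2.1 is the dosing instruction and addresses both routes in terms. The 20 mg/kg figure also stands in the Synopsis, Section 2.2 and SAP 1.1. On this view one background sentence is out of step with consistent dosing text, and a site that follows Section 7.2.1 breaks no dosing rule. That is correct, and it limits the point to reconciling the text. It does not remove the discrepancy, because no passage says why the rationale gives a lower figure for injection.

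Some stronger readings are tempting, and the documents do not support them:

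- **That sites cannot comply with both sections.** They can: a 1,000 mg infusion satisfies both, and the route is theirs to choose.
- **That no deviation code could capture a breach.** Appendix 1 has an open OTHER category, still to be classified as major or minor. What is missing is a specific code. Under the current text a dose given according to Table 2 is not a dosing-section deviation, so the absence of a 15 mg/kg code follows from Section 7.2.1.
- **That most lighter subjects are affected.** The interval from 50 to 66.7 kg covers 16.7 of the 20 kg between 50 and 70 kg. That is a width on the weight scale, not a share of subjects.
- **That subjects are being overdosed, or that dosing should pause.** Whether 15 mg/kg is a binding limit for injection depends on product information outside these documents.

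**Conclusion.** The inconsistency is real and should be resolved. Section 2 and Section 7.2.1 give different maxima for undiluted injection, and a 1,000 mg injection at 50 to under 66.7 kg lies between them, at just over 15 and up to 20.0 mg/kg. It is more than a clerical matter because it concerns a maximum dose of the study drug and bears on the overdose definition.

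The number of subjects concerned cannot be computed: the documents give neither the weight distribution nor the share of FCM doses that are injected. If every 1,000 mg dose in that weight range is infused, it is zero. The sample size, margin, analysis sets and primary analysis are unaffected.

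The conclusion rests only on the stated ceilings, Table 2 and the freedom of route. It makes no assumption about which ceiling is correct.

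**What to change.** 1. Reconcile the Synopsis, Section 2, Section 2.2, Section 7.2.1 with Table 2, and SAP 1.1 against the sponsor's reference product information (Section 10.1.1 names the Investigator's Brochure as the reference safety information for FCM). One maximum per route should then be stated consistently throughout. The choice of figure is for the sponsor.
2. Make the overdose definition in Protocol 10.1.7 and SAP 4.7.1 point to that reconciled maximum.
3. Align the FCM dosing codes in SAP Appendix 1 with the reconciled text, so that a breach of a route-specific maximum, if one is retained, does not depend on the OTHER category.
4. Add to the exposure table (SAP 4.5) the FCM dose in mg/kg by route of administration.

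**Cost.** A protocol clarification or amendment, a letter to sites, and one added summary. The summary needs weight, dose form and volume. Weight is measured at screening, and SAP 4.5 lists dose form and volume administered. The sponsor should confirm that the dose-form field distinguishes injection from infusion, since the documents do not say so in terms.
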